### 4.2 *Describe any primary or secondary safety endpoints. These should be included for all studies that are greater than minimal risk.*

- Primary: No significant difference in ocular hypertension 1-2 weeks post-operatively, defined as IOP of >5mmHg above baseline
- Secondary:
  - No significant difference in infections following surgery
  - No significant difference in hypersensitivity following surgery

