## Using Triamcinolone Acetonide to Reduce Pain after Scleral Buckle Surgery

will be given appointments for post-operative day 1, and 1-2 weeks post-operative as is standard practice.

On post-operative day one, primary outcome data will be obtained by a blinded examiner who will be giving the patient a form which asks about the patient's pain score by reference to an 11-point numbered rating scale (0-10). On the same form, patients will also be asked about post-operative nausea and vomiting for secondary endpoint, which will be scored from 0-6 by adding the points for question II and question III from the pain and nausea survey. The form will be collected by the same examiner when completed. Pill count sheet will be collected and additional sheet will be given for patient to track analgesic use between first and second visit.

Patient will then have regularly scheduled visit with the surgeon who will be screening the patient for success of surgery, adverse events, and will examine pain and nausea scores to ensure both are well controlled. The physician will be ensuring the patient's safety, and will be allowed to prescribe any medications deemed medically necessary for control of side effects, nausea, and pain. IOP of all patients will also be measured at this visit.

At second post-operative visit (1-2 weeks), patients' IOP will be measured again for safety endpoint. Patient pill count sheet will be collected.

Patients will be filling out 11-point NRS pain score and post-operative nausea and vomiting sheet again during office visit and it will be collected by blinded examiner. Patient will then be examined by surgeon again for success of surgery, adverse events, and control of pain and nausea.

	Before Surgery	Day of Surgery	Between Surgery and First Follow-Up Visit	First Follow-Up Visit (1 day after surgery)	Between 1 st and 2 nd Follow-Up Visits	Second Follow-Up Visit (1-2 weeks after surgery)	Long-Term Follow-Up (6 months )
Location	Clinic	Surgery Center	Home	Clinic	Home	Clinic	Phone
Procedures	The doctor will explain the study to patient	Everyone: Scleral Buckle Surgery. Experimental Group: Triamcinolone (steroid) will be applied during surgery. Control Group: Saline solution will		Everyone : will be examined by the doctor for safety		Everyone : will be examined by the doctor for safety	

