### 8.2 *Describe:*

- *Procedures or safeguards intended to reduce the probability and magnitude of risks.*

Patients will be screened twice for IOP (measured by tonometer) post-surgically to check for ocular hypertension. Patients eyes will also be examined at both visits by the primary surgeon via slit-lamp to determine any adverse events as a result of surgery or the intervention. The surgeon is responsible for the medical safety of all patients and may prescribe any medications deemed necessary for control of side effects of surgery or intervention, including nausea and vomiting.

- *Be sure to describe all drugs and devices used in the research, when they will be administered or used, and their purpose.*  
See 7.1

*Methods used to collect data about subjects. Please upload all data collection forms to Protocol Management*

- Pain and Nausea Survey
- Pill-Count
- IOP (tonometry)

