### 8.3 *What data will you collect during the study and how you will obtain them? Please include descriptions of electronic data collection, database matching, and app-based data collection.*

Patients will be assigned an arbitrary patient ID at beginning of the study which is recorded in the EMR. Demographic data about patient age, gender, and ethnicity will be extracted from the electronic medical record. No patient identifying data including name, addresses, date of birth, or

SSN will be extracted from the electronic medical record for the purpose of the analysis. Details of surgery will be extracted from the EMR.

During the study, IOP will be collected at two time-points via tonometer. This data will be extracted from the electronic medical record for analysis. Pain level via 11-pt NRS will be collected at two time points by survey. Data about analgesic consumption will be collected via survey form at two time points by survey. Nausea and vomiting score will be collected at two time points by survey. This data will be matched to de-identified patient ID. Physical survey forms will then be confidentially discarded.

*8.4 Who will transcribe or code audio and/or video recordings?*

N/A

*8.5 Include a description of any deception to be used in the study.*

N/A

*8.6 If the study involves long-term follow-up (once all research related procedures are complete), describe what data will be collected during the follow up period and when it will occur.*

N/A

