## Using Triamcinolone Acetonide to Reduce Pain after Scleral Buckle Surgery

used. Corticosteroids may enhance the establishment of secondary ocular infections due to fungi or viruses. If an infection occurs during corticosteroid therapy, it will be promptly controlled by suitable antimicrobial therapy.

**Elevated Intraocular Pressure:** Increases in intraocular pressure associated with triamcinolone acetonide injection have been observed in 20-60% of patients. This may lead to glaucoma with possible damage to the optic nerve. Effects on intraocular pressure may last up to 6 months following injection and are usually managed by topical glaucoma therapy. A small percentage of patients may require aggressive non-topical treatment. Intraocular pressure as well as perfusion of the optic nerve head will be monitored and managed appropriately. As our study will be irrigating the peribulbar space rather than injecting into the posterior capsule of the eye, we expect our rate of elevated IOP to be much lower than that determined by the FDA.

**Endophthalmitis:** The rate of infectious culture positive endophthalmitis is 0.5%. Proper aseptic techniques will always be used when administering triamcinolone acetonide. In addition, patients will be monitored following the injection to permit early treatment should an infection occur.

**Cataracts:** Use of corticosteroids may produce cataracts, particularly posterior subcapsular cataracts. As our study will be irrigating the subtenon's space rather than injecting into the posterior capsule of the eye, we expect our rate of cataracts to be much lower than that determined by the FDA.

**Patients with Ocular Herpes Simplex:** Corticosteroids should be used cautiously in patients with ocular herpes simplex because of possible corneal perforation. Corticosteroids should not be used in active ocular herpes simplex. We will be excluding all patients with ocular herpes simplex.

Systemic reactions are exceedingly rare in ophthalmic administration of corticosteroids but are included below for completeness:

**Cardiovascular:** Bradycardia, cardiac arrest, cardiac arrhythmias, cardiac enlargement, circulatory collapse, congestive heart failure, fat embolism, hypertrophic cardiomyopathy in premature infants, myocardial rupture following recent myocardial infarction, pulmonary edema, syncope, tachycardia, thromboembolism, thrombophlebitis, vasculitis

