### 21.1 Describe:

- *The plan to periodically evaluate the data collected regarding both harms and benefits to determine whether subjects remain safe (e.g., periodic reporting to the IRB, establishing a data monitoring*

*committee, reporting data monitoring committee findings to the IRB and the sponsor).*

The patient's IOP will be measured at baseline prior to the surgery, as well as 24 hrs post-op and 2 weeks post-op. This is done to monitor ocular hypertension, a potential side-effect of both the surgery and TA treatment. Patients will also have two normally scheduled follow-up visits with the surgeon who will be monitoring for any other adverse events such as hypersensitivity or infection. If adverse events occur that may be related to the intervention, they will be reported to the IRB promptly. The data will also be monitored after every 10th patient completes the protocol for any statistically significant differences in the primary or secondary safety endpoints. If this occurs, it too will be reported to the IRB promptly.

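### The primary safety endpoint scores an IOP rise that was treated or resolved before the 1-2 week visit as no ocular hypertension, and IOP-lowering treatment is not recorded

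*Combined protocol and SAP*

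**What the plan says.** Section 4.2 gives the primary safety endpoint: "Primary: No significant difference in ocular hypertension 1-2 weeks post-operatively, defined as IOP of >5mmHg above baseline". Section 8.1 ties it to one reading: "At second post-operative visit (1-2 weeks), patients' IOP will be measured again for safety endpoint". Day-1 pressure is also taken ("IOP of all patients will also be measured at this visit"), and section 21.1 gives the whole schedule: "The patient's IOP will be measured at baseline prior to the surgery, as well as 24 hrs post-op and 2 weeks post-op". No endpoint uses the day-1 value.

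On treatment, section 8.1 says that from the day-1 visit the surgeon "will be allowed to prescribe any medications deemed medically necessary for control of side effects, nausea, and pain". Section 8.2 repeats that the surgeon "may prescribe any medications deemed necessary for control of side effects of surgery or intervention". Section 17.1 says of triamcinolone: "Effects on intraocular pressure may last up to 6 months following injection and are usually managed by topical glaucoma therapy". Section 8.1 states that the surgeon cannot be masked, and section 8.2 has the primary surgeon examine the eye at both follow-up visits.

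On data, section 8.2 lists the pain and nausea survey, the pill count and tonometry. Section 8.3 adds demographics and details of surgery, and says "During the study, IOP will be collected at two time-points via tonometer". The pill-count form covers analgesics. Neither section lists IOP-lowering treatment given after surgery. The analysis plan in section 5.2 does not mention the safety endpoints.

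**The concern.** Treatment that can start on day 1 acts on the measurement that defines harm one to two weeks later. Suppose a patient has a clear rise on day 1, is treated, and reads 3 mmHg above baseline at the second visit. Under section 4.2 this patient counts the same as one whose pressure never rose, and the extracted data would not show the difference.

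The endpoint is worded as an absence of significant difference, so lost events make the hoped-for finding easier to reach. Raised IOP is one of the two most common adverse events that section 17.1 names for this drug, and section 3.3 hopes that a positive result will help set a standard of care. The check after every tenth patient in section 21.1 uses the same safety endpoints and has the same gap.

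**Working it through.** **1. How the definition scores each course of IOP**

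| Course after surgery | Reading at 1-2 weeks | Scored under 4.2 |
|---|---|---|
| Rise, still present | more than 5 mmHg above baseline | event |
| Rise on day 1, resolves untreated | within 5 mmHg | no event |
| Rise on day 1, treated and controlled | within 5 mmHg | no event |
| Never raised | within 5 mmHg | no event |

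The last three rows are scored alike. The day-1 reading could separate the second and third rows from the fourth, but no endpoint uses it. Separating the second from the third needs treatment data, which are not listed.

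**2. The plan's own figure**

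The documents give no sample size, power or margin for the IOP endpoint. The only figure is N = 48 for pain (section 14.1: alpha 0.01, power 0.80, d = 1.05). It reproduces:

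- d = 2 / sqrt((1² + 2.5²)/2) = 2 / 1.904 = 1.05.
- A two-sided t-test needs 22.9, so 23 per arm, or 46 in total.
- With a Mann-Whitney efficiency of 0.955, 22.9 / 0.955 = 24.0, so 24 per arm, or 48.

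That figure is not in dispute. It is used here only for the expected arm size: 48 / 2 = 24.

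**3. Illustration of the loss**

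Assumptions, none of them from the documents: the true rates of a rise at any time in each arm, the share gone by the visit, and a two-sided 0.05 Fisher exact test. Section 17.1 gives 20-60% for injection and expects a much lower rate here.

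Observed rate = true rate × (1 − share gone by the visit).

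For 40% versus 10%:

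- None gone: 40% versus 10%, power 60%.
- Half gone in both arms: 0.40 × 0.5 = 20% versus 0.10 × 0.5 = 5%, power 24%.
- Half gone in the triamcinolone arm only: 20% versus 10%, power 10%.

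Other assumed rates, with half gone in both arms:

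| True rates, triamcinolone vs control | Power, all rises counted | Power, 1-2 week reading only |
|---|---|---|
| 20% vs 5% | 24% | 5% |
| 40% vs 5% | 82% | 36% |
| 60% vs 5% | 99% | 72% |
| 40% vs 20% | 24% | 10% |
| 60% vs 20% | 76% | 31% |

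Equal loss in both arms is enough to reduce power. Different treatment by arm is not needed.

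**4. Should day-1 rises be merged into the event?**

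Section 21.1 says that surgery itself can raise IOP. Let a share s of patients in both arms have an independent surgical rise on day 1. The merged rate is 1 − (1 − true rate)(1 − s). Starting from 40% versus 10%:

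- s = 10%: 46% versus 19%, power 42%.
- s = 20%: 52% versus 28%, power 31%.
- s = 30%: 58% versus 37%, power 24%.

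Merging can cost as much power as the gap it closes, so day-1 rises are better reported separately.

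**The case against.** A pressure reading at a fixed time under usual care is a legitimate measure: it shows where patients stand with treatment available. Day-1 IOP is measured in everyone and, on the natural reading of section 8.3, is already extracted. Adverse events that may be related go to the IRB (section 21.1). The pain result is unaffected. All of this stands, and it limits the severity. It does not close the gap, because individual reports are not a comparison between arms, and without treatment data a reading on treatment cannot be told from an untreated normal one.

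The opportunity for loss is also limited. The schedule in section 8.1 has patients at home between day 1 and the second visit, so day 1 is the only planned occasion to start treatment before the endpoint reading. A later rise is lost only through an unscheduled contact or if it resolves by itself. Section 17.1 says effects may last up to six months, so untreated rises may well persist and be counted. The share of one half above is therefore an assumption that could be too high.

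A reader might infer three stronger points that the documents do not support:

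- That every day-1 rise is ignored. Only a rise that is back within 5 mmHg of baseline at 1-2 weeks is lost.
- That the unmasked surgeon will treat the arms differently and so hide or reverse an excess. The documents show that this is possible, not that it happens, and its direction is uncertain. A reversal needs an assumed, strongly unequal split.
- That two IOP time points in section 8.3 are too few for the current endpoint. That endpoint needs two readings, baseline and 1-2 weeks. The narrower point is that, if the two are the post-operative readings, baseline is measured (section 21.1) but not listed for extraction.

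**Conclusion.** The point holds as a should-fix. As written, the plan scores a rise that was treated and controlled, or that resolved, before the 1-2 week visit as no ocular hypertension, and it does not collect the treatment data needed to recognise the treated cases. A real excess with triamcinolone could then pass as no significant difference.

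The size is unknown. With assumed rates of 40% versus 10%, 24 per arm and half the rises gone in both arms, power falls from 60% to 24%. With none treated or resolved, the loss is zero. The conclusion rests on the definition in section 4.2 and the data lists in sections 8.2 and 8.3. It does not rest on these rates or on any claim that the surgeon treats the arms differently.

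**What to change.** **Section 8.3.** Add two items to the EMR extraction, alongside the day-1 and 1-2 week readings: baseline IOP, and any IOP-lowering treatment started after surgery up to the 1-2 week visit.

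**Section 4.2.** Keep the 1-2 week time point. Count a patient as having an event if IOP is more than 5 mmHg above baseline at that visit, or if IOP-lowering treatment was started after surgery and before it. Report separately by arm: the 1-2 week reading alone, treatment started, and day-1 IOP more than 5 mmHg above baseline. Do not merge day-1 rises into the primary safety event.

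**Cost.** Some wording and a few EMR fields, with no added visit or measurement and no change to clinical management. The items should be specified before extraction, since section 9.4 has the re-identification code destroyed after publication.

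**Downside.** The treatment component depends on the decision of an unmasked surgeon and can bias the comparison the other way, which is why the components are shown separately. A rise that resolves untreated still falls outside the event; if present on day 1, it appears in the day-1 report.

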## 5.0 Study Design and Statistical Analysis Plan

*5.1 Describe the basic study design/approach*

Simple randomized controlled trial comparing two groups in reducing post-operative pain from scleral buckle surgery -

1. Peribulbar irrigation of triamcinolone acetonide (Experimental Group)
2. Balanced Salt Solution (Control Group)

*5.2 Describe corresponding data analysis plan/approach*

Parametric analysis of experimental and control groups using students' t-test for primary endpoint, secondary endpoint of pain and analgesic consumption will be analyzed similarly. Secondary endpoints of nausea and vomiting score will be analyzed via non-parametric analysis (Mann-Whitney U test)

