### 12.2 Describe the eligibility criteria that define who will be included and who will be excluded from enrollment for each procedure of your study.

Inclusion Criteria: Patient must have rhegmatogenous retinal detachment and be scheduled to undergo scleral buckle surgery for correction.

Exclusion Criteria:

- Patient under 18 years old
- Advanced Glaucoma
- History of corticosteroid responsive elevation in IOP
- Allergy to Triamcinolone Acetonide or other corticosteroids
- Pre-existing chronic pain disorders
- Herpes zoster
- Prior corneal allograft
- Allergy to local anesthetic or penicillin

- Patients unable to consent on own behalf
- Patients unable to communicate pain and nausea levels
- Pregnancy
- Incarceration

*12.3 Indicate specifically whether you will include or exclude each of the following special populations: (You may not include members of these populations as subjects in your research unless you indicate them in the description of your subject population.)*

All of the following populations will be excluded from our study.

- *Minors, as defined by state law where the study is performed (infants, children, teenagers)*
- *Pregnant women*
- *Prisoners (including all incarcerated individuals)*
- *Adults not capable to consent on their own behalf*

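### The primary safety endpoint reduces IOP to a relative cut of more than 5 mmHg, with no absolute level and no planned analysis in mmHg, so the label can mislead and a pressure effect is harder to detect

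*Combined protocol and SAP*

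**What the plan says.** Section 4.2 states the primary safety endpoint as "No significant difference in ocular hypertension 1-2 weeks post-operatively", "defined as IOP of >5mmHg above baseline". Section 21.1 fixes the reference value and the schedule: "The patient's IOP will be measured at baseline prior to the surgery, as well as 24 hrs post-op and 2 weeks post-op". Section 8.3, on data to be extracted, says that "IOP will be collected at two time-points via tonometer".

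Section 12.2 puts no numeric limit on baseline IOP. Its IOP-related exclusions are "Advanced Glaucoma" and a history of steroid-responsive pressure rise, so eyes with low or fairly high pressure can both enter.

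Section 5.2 begins "Parametric analysis of experimental and control groups using students' t-test for primary endpoint" and goes on to analgesic use and the nausea score. It names no method for IOP, either as a proportion or in mmHg. Section 17.1 says "Increases in intraocular pressure associated with triamcinolone acetonide injection have been observed in 20-60% of patients", and then, because the route differs, "we expect our rate of elevated IOP to be much lower than that determined by the FDA". It gives no figure for the expected rate and no definition of the rise behind the 20-60%.

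**The concern.** Raised pressure is one of the two most common adverse events that section 17.1 reports for this drug, and the same section links it to glaucoma and optic nerve damage. The trial will hold each patient's pressure in mmHg before and after surgery, yet the only comparison it defines is yes or no on a rise of more than 5 mmHg.

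Two things follow. First, the label and the pressure can disagree, because only the difference from baseline counts. Second, a cut on a continuous measure discards information, and here the cost falls in one direction. The stated goal is an absence of significance with no margin, so a less sensitive comparison is more likely to be read as reassurance. Section 21.1 also looks at the safety endpoints after every tenth patient, when numbers are smaller still.

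**Working it through.** **The plan's own figure.** The only sized endpoint is pain (section 14.1): d = 2/√((1² + 2.5²)/2) = 2/1.904 = 1.05, alpha 0.01, power 0.80. A two-sided t-test needs 22.9 per arm. Dividing by the Mann-Whitney efficiency 3/π gives 23.98, so 24 per arm and 48 in total. The stated 48 reproduces, but it was not set for IOP.

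**Classification.** This is arithmetic on the definition; the pressures are illustrations.
- 8 to 14 mmHg: change +6, more than 5, an event.
- 22 to 27 mmHg: change +5, not more than 5, no event.

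The documents give no IOP distribution, so they cannot say how often either case occurs.

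**Information lost by the cut.** For a normally distributed change and event rate p, the efficiency of the cut relative to simple change is φ(z_p)²/[p(1−p)], where z_p is the normal quantile at p and φ the normal density.

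| Event rate | Efficiency | Loss |
|---|---|---|
| 5% | 0.224 | 78% |
| 10% | 0.342 | 66% |
| 15% | 0.426 | 57% |
| 20% | 0.490 | 51% |
| 21% | 0.501 | 50% |
| 50% | 0.637 | 36% |
| 60% | 0.622 | 38% |

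The smallest loss is 36%, at a 50% rate. The loss passes one half below about 21%.

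Against a baseline-adjusted analysis, the efficiency is multiplied by (1+ρ)/2, where ρ is the baseline to follow-up correlation (equal variances assumed). With ρ from 0.3 to 0.7, the loss at a 20% rate is 1 − 0.490 × 0.85 = 58% to 1 − 0.490 × 0.65 = 68%. At a 50% rate it is 46-59%.

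**Power, uniform effect.** All inputs are assumptions: 24 per arm, two-sided 0.05 (the plan states no alpha for safety), normal change, no mean change in controls, and the same shift in every treated eye. Event rates are 1 − Φ(5/SD) in controls and 1 − Φ((5 − effect)/SD) in treated eyes.

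| SD (mmHg) | Effect (mmHg) | Event rates | t-test on mmHg | Fisher on the cut |
|---|---|---|---|---|
| 4 | 2 | 11% v 23% | 40% | 13% |
| 4 | 3 | 11% v 31% | 72% | 32% |
| 4 | 4 | 11% v 40% | 92% | 58% |
| 5 | 2 | 16% v 27% | 27% | 10% |
| 5 | 3 | 16% v 35% | 53% | 23% |
| 5 | 4 | 16% v 42% | 77% | 42% |
| 6 | 2 | 20% v 31% | 20% | 8% |
| 6 | 3 | 20% v 37% | 40% | 17% |
| 6 | 4 | 20% v 43% | 62% | 31% |

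For 80% power at SD 5 and effect 3, the cut needs 85 per arm against 44 for simple change.

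**Power, responders only.** Suppose a fraction of treated eyes rises by 10 mmHg and the rest do not (SD 4). Power on mmHg v the cut is 27% v 20% at a fraction of 20%, 50% v 41% at 30%, and 73% v 64% at 40%. The gap is about 7-9 points.

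**Recovery in both arms.** Add a mean rise of 3 mmHg to each arm, keeping an effect of 4 mmHg. Control event rates become 1 − Φ(2/4) = 31% and 1 − Φ(2/5) = 34%. Fisher power rises from 58% to 71% at SD 4 and from 42% to 50% at SD 5. It stays below the 92% and 77% available on mmHg.

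**The case against.** A rise from baseline is a coherent safety measure, an event rate is easier to read clinically than a mean difference, and randomisation balances baseline IOP in expectation, so the definition favours neither arm. That stands, and it is why the proportion should be kept. Whether to add an absolute-pressure criterion is partly preference.

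Section 17.1 describes pressure elevation as something that happens to some patients, not as a shift in all. On that pattern the gain from mmHg is modest, as the responder calculation shows. Treatment of raised pressure before the 1-2 week reading, which section 8.1 leaves to the surgeon, would affect a mean as well as a proportion. Both points stand and limit the size of the concern.

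Four stronger readings are tempting, and the documents do not support them:
- **False events from recovery dilute the comparison.** In the model above, recovery in both arms raises the power of the cut. The damage is to the meaning of the label.
- **Most of the information or power is lost.** This is not true unconditionally. Against simple change, the loss is 36-50% at event rates of 21-60%.
- **The endpoint rests on a single handheld reading.** No section says how many readings are taken per visit. A handheld device is named only for screening in section 8.1; sections 8.2 and 8.3 say only tonometer.
- **Baseline pressure will be unusually low.** That is an assumption. Eyes can be misclassified, but the documents do not show that many will be.

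The two time points in section 8.3 may simply mean the two post-operative visits. That makes it a wording matter.

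**Conclusion.** The concern holds in a limited form. The endpoint is relative only, assessed at one visit, with no absolute level and no planned mmHg analysis, so the mismatch between label and pressure follows directly from the definition.

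The loss of at least about a third of the information rests on normality of the change. Whether it exceeds half depends on the event rate. The protocol's expectation of a rate well under 20-60% makes that plausible without establishing it. Every power figure rests on assumed SDs and effects. The mmHg analysis did better in each scenario computed, by margins from about 7 points to about 40. The practical consequence is that a finding of no significant difference would carry less reassurance than the collected data could give.

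**What to change.** In sections 4.2 and 5.2, add the between-arm difference in IOP (mmHg) at 1-2 weeks, adjusted for baseline IOP by linear regression on arm and baseline, reported with its 95% confidence interval. Keep the proportion more than 5 mmHg above baseline alongside it. Report by arm any pressure-lowering treatment given before the reading, since it can affect both measures.

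In section 8.3, state that the pre-operative IOP is extracted as well, and reconcile the wording with section 21.1. Whether to add an absolute-pressure criterion, and at what level, is for the investigators to decide before data are seen.

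The cost is wording in three sections, slightly more analysis work, and one item on pressure-lowering treatment taken from the medical record. All the IOP readings are already scheduled. The small downside is that a mean difference is less directly clinical than an event rate, which keeping the proportion addresses.
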